- g Vital signs include body temperature, blood pressure, and pulse. Blood pressure and pulse will be measured in triplicate in the sitting position and should be measured prior to blood draws.
- h The C-SSRS and SHSF (SHFU when applicable) will be completed at scheduled and unscheduled office visits.
- i At V1, record AEs that are on-going from the previous trial.
- j Patients should remain in the office for 30 minutes of observation following the first LY2951742 injection of the study; injections of LY2951742 are to occur after all other visit procedures are completed.
- k May be repeated during the study at the discretion of the investigator.

3. Introduction

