3.3. Benefit/Risk Assessment

More information about the known and expected benefits, risks, and reasonably anticipated AEs of galcanezumab may be found in the IB. Information on AEs expected to be related to the investigational product may be found in Section 7 (Development Core Safety Information) of the IB. Information on SAEs expected in the study population independent of drug exposure and that will be assessed by the sponsor in aggregate periodically during the course of the study, may be found in Section 6 (Effects in Humans) of the IB.

4. Objectives and Endpoints

Table 4.1 shows the objectives and endpoints of the study.

Table 4.1. Objectives and Endpoints

Objectives	Endpoints

Primary To evaluate the safety of open-label galcanezumab within the context of expected medical practice in eligible patients with episodic or chronic cluster headache.
	
Analysis of:
 
 • TEAEs • SAEs • Suicidal ideation and behaviors assessed by solicited questioning using the C-SSRS

Secondary To characterize the reasons for discontinuation and AEs of interest for galcanezumab. To characterize the immunogenicity of galcanezumab.
	
Discontinuation rates
 
Analysis of:
 
 • Injection-site reactions • Allergy/hypersensitivity • Infections • The development and consequences of ADAs to galcanezumab, their relationship with AEs, and neutralizing ADAs to galcanezumab

Tertiary To evaluate the effectiveness of galcanezumab. To evaluate the effect of galcanezumab on health values.
	
 • The proportion of patients reporting a score of 1 (“very much better”) or 2 (“much better”) on the PGI-I 1 month after receiving their first dose will be reported. 
EQ-5D-5L Analysis of:
 
 • Health state index values • Each dimension of the descriptive system and dichotomized level responses • EQ-VAS current health score • Correlations with PGI-I, cluster headache status

Abbreviations: ADA = anti-drug antibodies; C-SSRS = Columbia-Suicide Severity Rating Scale; EQ-5D-5L Analysis = European quality 5-dimensions 5-levels; EQ-VAS = European Quality Visual Analogue Scale; PGI-I = Patient Global Impression of Improvement; SAE = serious adverse event; TEAE = treatment-emergent adverse event.

5. Study Design

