Note: After V1, if V2 does not occur within 3 months of V1 (e.g., patient enters V1 in remission), prior to V2 an ECG, hematology, clinical chemistry, urinalysis, urine drug screen (UDS), HbA_{1C}, and serum pregnancy must be collected and eligibility confirmed prior to dosing at V2 (see footnote “d” in the SOA).

Study Phase II: SP II is the single-arm open-label treatment phase during which patients can receive galcanezumab 300 mg administered SC up to once a month. If a patient meets all eligibility requirements, a urine pregnancy screen will be conducted at the first dosing visit, prior to dosing to confirm that a female patient is not pregnant before administering investigational product. Following the first dose of galcanezumab, the patient should remain in the office for 30 minutes of observation. The site will have a scheduled telephone visit (V3) with the patient approximately 1 week after the first investigational product administration to collect spontaneously reported AEs.

Every month, the decision whether to administer a monthly dose will be based upon the study investigator’s judgment, which is not limited to, but includes assessment of the patient’s clinical symptoms and response as follows:

- Dosing is up to once monthly; more frequent dosing is not allowed. The full 300 mg dose is to be administered, changing the dose amount is not allowed.
- If the patient remits and dosing is halted, the patient may remain in the study, but they should have an office visit 1 month after the last dose to complete the procedures listed in

Event List F (Table 2.1). Dosing in this scenario may be reinitiated at the study investigator's discretion.

- Monthly telephone visits should be completed for patients who are not being dosed, but remain in the study (e.g., in remission).
- If dosing is temporarily interrupted due to a potential safety concern, dosing may be reinitiated at the study investigator's discretion following a discussion and agreement between the study investigator and Lilly Medical that re-initiation of dosing is appropriate.
 - At the office visit **prior to re-initiation of dosing** the following procedures: ECG, immunogenicity, pharmacokinetics (PK), hematology, clinical chemistry, HbA1c and urine pregnancy are to be collected. The urine pregnancy must be negative and the ECG should be evaluated for safety prior to dosing.

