5.16.5. Suicide-Related Thoughts and Behaviors

Postbaseline suicidal ideation, suicidal behavior, and self-injurious behavior without suicidal intent, based on the C-SSRS, will be summarized for the GMB-treated population during GMB-treated time and GMB-treated time plus post-treatment time. In particular, for each of the following events, the number and percent of patients with the event will be enumerated: completed suicide, nonfatal suicide attempt, interrupted attempt, aborted attempt, preparatory acts or behavior, active suicidal ideation with specific plan and intent, active suicidal ideation with some intent to act without specific plan, active suicidal ideation with any methods (no plan) without intent to act, nonspecific active suicidal thoughts, wish to be dead, and self-injurious behavior without suicidal intent.

In addition, the number and percent of patients who experienced at least one of various composite measures will be presented and compared. These include suicidal behavior (completed suicide, non-fatal suicidal attempts, interrupted attempts, aborted attempts, and preparatory acts or behavior), suicidal ideation (active suicidal ideation with specific plan and intent, active suicidal ideation with some intent to act without specific plan, active suicidal ideation with any methods [no plan] without intent to act, non-specific active suicidal thoughts, and wish to be dead), and suicidal ideation or behavior.

Specifically, the following outcomes are C-SSRS categories and have binary responses (yes/no). The categories have been re-ordered from the actual scale to facilitate the definitions of the composite and comparative endpoints, and to enable clarity in the presentation of the results.

Category 1 – Wish to be Dead

Category 2 – Non-specific Active Suicidal Thoughts

Category 3 – Active Suicidal Ideation with Any Methods (Not Plan) without Intent to Act

Category 4 – Active Suicidal Ideation with Some Intent to Act, without Specific Plan

Category 5 – Active Suicidal Ideation with Specific Plan and Intent

Category 6 – Preparatory Acts or Behavior

Category 7 – Aborted Attempt

Category 8 – Interrupted Attempt

Category 9 – Actual Attempt (non-fatal)

Category 10 – Completed Suicide

Self-injurious behavior without suicidal intent is also a C-SSRS outcome (although not suicide-related) and has a binary response (yes/no).

Composite endpoints based on the above categories are defined below.

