- Suicidal ideation: A “yes” answer at any time during treatment to any 1 of the 5 suicidal ideation questions (Categories 1-5) on the C-SSRS.
- Suicidal behavior: A “yes” answer at any time during treatment to any 1 of the 5 suicidal behavior questions (Categories 6-10) on the C-SSRS.
- Suicidal ideation or behavior: A “yes” answer at any time during treatment to any 1 of the 10 suicidal ideation and behavior questions (Categories 1-10) on the C-SSRS.

Patients who discontinued from the study with no postbaseline C-SSRS value will be considered unevaluable for analyses of suicide-related events. Only evaluable patients will be considered in the analyses.

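### As SAP 5.16.5 is written, the primary C-SSRS table can omit a suicide, or an attempt with no later C-SSRS, that the SAE table shows, and nothing reconciles the two

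*SAP*

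**What the plan says.** Protocol Table 4.1 lists three primary endpoints: TEAEs, SAEs, and "Suicidal ideation and behaviors assessed by solicited questioning using the C-SSRS".

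SAP 5.16.5 builds the table for the third. The rows to be enumerated include "completed suicide, nonfatal suicide attempt, interrupted attempt, aborted attempt, preparatory acts or behavior", and the list of yes/no outcomes ends with "Category 10 – Completed Suicide". The suicidal behavior composite needs a 'yes' answer "at any time during treatment to any 1 of the 5 suicidal behavior questions (Categories 6-10) on the C-SSRS". The section closes with the evaluability rule: "Patients who discontinued from the study with no postbaseline C-SSRS value will be considered unevaluable for analyses of suicide-related events". It then adds: "Only evaluable patients will be considered in the analyses". There is no exception for death, or for an event known from an AE or SAE report.

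On timing, footnote h of Protocol Table 2.1 says that the C-SSRS and the self-harm form "will be completed at scheduled and unscheduled office visits". Event List G, the telephone visit, has AE and SAE collection but no C-SSRS. It is used about a week after the first dose. Under Protocol 5.1 it is also used monthly for patients who stay in the study without being dosed.

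The protocol itself sets no C-SSRS condition. Sections 10.2 and 10.3.1 place safety analyses on all patients with at least one dose, and 10.3.4 enumerates patients with each suicidality event.

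**The concern.** A patient normally enters this table by attending an office visit after dosing and answering the questionnaire. A patient who has died cannot do that. For the most severe row, the event itself can therefore cause the missing value that removes the patient. Where an earlier form exists, the event can leave a reassuring 'no' as the last word.

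The table reports a primary safety endpoint in a single-arm study, where the count is the result. A zero under completed suicide or suicidal behavior would be read as no such event having occurred. The SAE table could show one in the same report, and the SAP has no step that explains the difference.

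**Working it through.** The documents give no sample size, event count or suicidality rate, so there is no planned figure to reproduce. The check applies the rule to individual patients and then shows the effect on the count.

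**Step 1: when the first postbaseline C-SSRS can exist.**
- Month 0 (Event List B) includes a C-SSRS, but footnote j of Protocol Table 2.1 puts the injection after all other procedures. That form is baseline.
- The week-1 contact (Event List G) is a telephone visit without a C-SSRS.
- The next scheduled C-SSRS is at Month 1 (Event List C), or at the first office visit after a dose if no dose is given (Event List F).

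Every patient therefore has a window of about one month after the first dose with no scheduled postbaseline C-SSRS. Only an unscheduled office visit would shorten it.

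**Step 2: apply SAP 5.16.5 to three patients.**

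| Patient | Status under the rule | Count in table | Count if all dosed patients with the event are included |
|---|---|---|---|
| A: suicide after first dose, before any postbaseline C-SSRS | Unevaluable | 0/(N−1) | 1/N |
| B: suicide after at least one postbaseline C-SSRS answered 'no', e.g. in telephone-only months | Evaluable, no 'yes' | 0/N | 1/N |
| C: non-fatal attempt | Counted if a later C-SSRS records it; otherwise as A or B | 1/N, or 0/(N−1) or 0/N | 1/N |

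For A, death is taken to count as discontinuation. If it were not so classed, the count would be 0/N, still zero. For A and B it is assumed that nobody enters a C-SSRS form after the death. For B in undosed months, the omission concerns the analysis over the whole open-label phase. SAP 5.4 treats those months as off-treatment time, but as postbaseline in that analysis.

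**Step 3: size for patient A, over an assumed range of N.** One event is assumed, with no other unevaluable patients. Limits are exact (Clopper-Pearson) 95%. For 0/n the upper limit is 1 − 0.025^(1/n); for example, 1 − 0.025^(1/99) = 3.66%. For 1/N the limits are the beta quantiles B(0.025; 1, N) and B(0.975; 2, N−1).

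| Assumed N | Under the rule | Upper limit | Event counted | 95% CI |
|---|---|---|---|---|
| 50 | 0/49 | 7.25% | 1/50 = 2.00% | 0.05% to 10.65% |
| 100 | 0/99 | 3.66% | 1/100 = 1.00% | 0.03% to 5.45% |
| 200 | 0/199 | 1.84% | 1/200 = 0.50% | 0.01% to 2.75% |
| 300 | 0/299 | 1.23% | 1/300 = 0.33% | 0.01% to 1.84% |

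The change from one event to none does not depend on N. The intervals are only for scale: SAP 5.16.5 plans numbers and percentages for this table, without intervals.

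**Step 4: where else the event is recorded.** A death after dosing is an SAE (Protocol 9.2.1). Serious AEs, and AEs leading to discontinuation, that are elicited through the C-SSRS are also entered as AEs (Protocol 9.2.1.2). SAP 5.16 tabulates both classes. SAP 5.16.5 refers to neither source.

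**The case against.** The strongest reply is that the endpoint is defined by its instrument. Table 4.1 speaks of solicited questioning with the C-SSRS, and SAEs are a separate primary endpoint. Two tables with different stated sources may differ without either being wrong, and an any-source table goes beyond the protocol's definition. This stands in part. It is why the C-SSRS-only count should remain visible. It does not explain a row for completed suicide that the patient concerned cannot answer.

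A reader might infer that a suicide would vanish from the report. The documents do not support that: the death belongs in the SAE table, and an attempt that is serious or leads to withdrawal belongs in the SAE or discontinuation tables.

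A reader might also infer that anyone who attempts suicide and withdraws, or who does so during telephone-only months, is lost from the C-SSRS table. That is not supported either. Early discontinuers should complete Event List F, which includes the C-SSRS (Protocol 8.1 and 8.2). A patient who stays in the study has the C-SSRS at the next office visit. Loss requires that visit to be missed. SAP Appendix 1 lists discontinuing without the Event List F visit as an important deviation, so this is foreseen but is not the planned course.

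Finally, the existence of a completed-suicide category may mean that staff can fill in the form for a patient who has died. If so, that patient has a postbaseline value and is counted. The documents do not say, and the result should not depend on site practice.

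**Conclusion.** The concern holds in a limited form. Followed as written, the rule turns a suicide before the first postbaseline C-SSRS into 0/(N−1), and a later suicide without a subsequent form into 0/N, where 1/N occurred. A non-fatal attempt shares this fate only if no later C-SSRS is obtained. For one event and an assumed N of 50 to 300, the omitted proportion is 2.00% to 0.33%.

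This rests on three assumptions: no C-SSRS form is entered after a death, N lies in the range shown, and no other patients are unevaluable. How likely such an event is cannot be judged from the documents.

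The defect is a primary table that can be silent on an event shown in another table, without reconciliation. It also narrows the protocol's all-dosed safety population. The SAP revision history says that the section was added for consistency with the other Phase 3 cluster headache SAPs, but gives no reason for this rule. It should be corrected. It does not put the rest of the safety reporting in doubt.

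**What to change.** In SAP 5.16.5:

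1. Treat a dosed patient as evaluable if there is a postbaseline C-SSRS, or a postbaseline AE, SAE or death record of suicide or suicidal behavior.
2. Count such events in the matching C-SSRS category after medical review, footnoted by source so that the C-SSRS-only count can still be read off.
3. Apply the unevaluable status only to patients with neither.
4. Report how many dosed patients lack a postbaseline C-SSRS.
5. Reconcile the table with the SAE table, and state whether a form entered for a deceased patient counts.

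Both the evaluability rule and the numerator must change. Correcting evaluability alone would leave patient B as a non-event. The self-harm forms add little as a source here, because they are completed at office visits and the supplement form counts events recorded in the C-SSRS.

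The cost is SAP wording, modest programming on data already in the eCRF, and a brief medical review to assign categories. No visit or procedure changes. Reported suicidality can only stay the same or rise. The interim locks in SAP 5.17.1 do not list the C-SSRS table among their topics, so the change concerns the final lock. If that has passed, Protocol 10.3.1 allows the change and its justification to be given in the CSR.

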5.16.6. Vital Signs and Weight

Vital signs collected during the study include systolic and diastolic blood pressure (BP), pulse, and temperature. BP and pulse measurements will be taken when the patient is in a sitting position. Three measurements of sitting BP and pulse will be collected at approximately 30 to 60 second intervals at every office visit and the 3 sitting BP measurements and 3 pulse values will be averaged and used as the value for that visit.

Table CGAR.5.1 displays the criteria used to define categorical changes of interest in vital signs and weight. The last column of the table displays the patient population for each analysis based on baseline categories. The number and percent of patients meeting these criteria will be summarized.

The criteria to identify patients with treatment-emergent abnormal changes generally consist of 2 parts, an absolute threshold and a change from baseline amount.

- The absolute threshold in the criteria is based on 1) minimum postbaseline when the direction is low; 2) maximum postbaseline when the direction is high.

- The change from baseline amount in the criteria is 1) decrease from baseline to minimum postbaseline when the direction is low; 2) increase from baseline to maximum postbaseline when the direction is high.

The baseline for systolic BP, diastolic BP, and pulse is defined as the last non-missing baseline value during the baseline period.

For categorical changes of interest in temperature and weight, the baseline values are defined below:

- For the analyses of categorical changes of interest in temperature and weight,
 - the baseline is defined as the minimum value during baseline period when the direction is low
 - the baseline is defined as the maximum value during the baseline period when the direction is high

Table CGAR.5.1. Categorical Changes of Interest in Vital Signs and Weight

Parameter	Direction	Criteria	Patients Population defined by Baseline Categories
Systolic BP (mm Hg) (sitting)	Low	≤ 90 and decrease ≥ 20	> 90 ; ≤ 90 ; All patients
	High	≥ 140 and increase ≥ 20	< 140 ; ≥ 140 ; All patients
	PCS High	≥ 180 and increase ≥ 20	< 180 ; ≥ 180 ; All patients
	Sustained Elevation	≥ 140 and increase ≥ 20 at 2 consecutive visits	< 140 ; ≥ 140 ; All patients
Diastolic BP (mm Hg) (sitting)	Low	≤ 50 and decrease ≥ 10	> 50 ; ≤ 50 ; All patients
	High	≥ 90 and increase ≥ 10	< 90 ; ≥ 90 ; All patients
	PCS High	≥ 105 and increase ≥ 15	< 105 ; ≥ 105 ; All patients
	Sustained Elevation	≥ 90 and increase ≥ 10 at 2 consecutive visits	< 90 ; ≥ 90 ; All patients
Systolic BP or Diastolic BP (mm Hg) (sitting)	Sustained Elevation	Meeting criteria for systolic BP for 2 consecutive visits or meeting criteria for diastolic BP for 2 consecutive visits or both	All patients
Pulse (bpm) (sitting)	Low	< 50 and decrease ≥ 15	≥ 50 ; < 50 ; All patients
	High	> 100 and increase ≥ 15	≤ 100 ; > 100 ; All patients
	Sustained Elevation	> 100 and increase ≥ 15 at 2 consecutive visits	≤ 100 ; > 100 ; All patients
Weight (kg)	Low	(Loss) decrease $\geq 7\%$	All patients
	High	(Gain) increase $\geq 7\%$	All patients
Temperature ($^{\circ}$ F)	Low	$< 96^{\circ}$ F and decrease $\geq 2^{\circ}$ F	$\geq 96^{\circ}$ F
	High	$\geq 101^{\circ}$ F and increase $\geq 2^{\circ}$ F	$< 101^{\circ}$ F

Abbreviations: BP = blood pressure; PCS = Potentially Clinically Significant; mm Hg = millimeters of mercury; bpm = beats per minute; kg = kilograms; ° F = degrees Fahrenheit.

5.16.7. Electrocardiogram Intervals and Heart Rate

Analyses of QTc interval, Fridericia's corrected QT interval (QTcF) (msec), will be calculated with Fridericia's formula as $QT/RR^{1/3}$. For the QTc calculations, the unit for QT is milliseconds and the unit for RR is seconds. For patients with QRS ≥ 120 milliseconds at any time during the study, the QT and QTc interval will be excluded from the analyses.

The baseline for ECG is defined as the last non-missing baseline value during the baseline period. This baseline definition for ECG applies to all analyses (quantitative and qualitative).

The number and percent of patients meeting criteria for treatment-emergent abnormalities in ECG intervals (PR, QRS, and QTcF) and heart rate will be summarized.

Table CGAR.5.2 displays the criteria for treatment-emergent changes in ECG intervals and heart rate.

- For treatment-emergent low analyses: patients with normal or high values at baseline (no low values) will be included.
- For treatment-emergent high analyses: patients with normal or low values at baseline (no high values) will be included.
- For treatment-emergent increase analyses: patients with a baseline and at least one postbaseline result will be included.

Table CGAR.5.2. Criteria for Treatment-Emergent Changes in ECG Intervals and Heart Rate

Parameter	Direction	Criteria	
Heart Rate (bpm)	Low	<50 and decrease ≥ 15	
	High	>100 and increase ≥ 15	
PR Interval (msec)	Low	<120	
	High	≥ 220	
QRS Interval (msec)	Low	<60	
	High	≥ 120	
QTcF (msec)	Low	Males: <330	Females: <340
	High	Males: >450	Females: >470
	PCS High	>500msec	
	Increase	Increase >30 msec	
Increase >60 msec			
Increase >75 msec			

Abbreviations: bpm = beats per minute; ECG = electrocardiogram; PCS = Potentially Clinically Significant; QTcF = Fridericia's corrected QT interval.

In addition, qualitative ECG abnormalities will be evaluated which will include 11 ECG categories (axis, rhythm, conduction, ischemia, infarction, injury, morphology, U-waves, T-waves, ST Segment, and other abnormalities) of qualitative findings. A category is a collection of possible descriptions (findings) of one qualitative aspect of an ECG. A category name is the name of the qualitative aspect of the ECG (for example, rhythm, conduction, morphology, ischemia, and so forth). A finding is one of the possible specific descriptions (for example, sinus bradycardia, acute septal infarction) within a category.

A shift table summary of qualitative ECGs at any time will be produced, to assess shifts from baseline normal to postbaseline abnormal for the overall ECG and for each of the 11 finding categories mentioned above.

Patients with the following are excluded from ECG analyses: lead reversals or <9 leads, nonmatching demographic data, and those suggesting patient identification errors.

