6.2. Exclusion Criteria

Patients will be excluded from study enrollment if they meet any of the following criteria:

7. Current enrollment in, or discontinuation within the last 30 days prior to V1 from, a clinical trial (with the exception of Study CGAL or Study CGAM) involving any investigational product or device, or concurrent enrollment in any other type of medical research judged not to be scientifically or medically compatible with this study.
 - a. Adequate washout (≥ 5 half-lives) of any investigational product is also required and may require >30 days depending on the half-life of the investigational product.
8. Use of therapeutic antibodies (except galcanezumab) during the course of the study (adalimumab, infliximab, trastuzumab, bevacizumab, etc.). Prior use of other therapeutic antibodies is allowed if an adequate washout has occurred (≥ 5 half-lives) prior to V2.
9. Lifetime history of migraine variants that could implicate or could be confused with ischemia; specifically, hemiplegic (sporadic or familial) migraine, ophthalmoplegic migraine, and basilar-type migraine defined by ICHD-3 beta.
10. Taking excluded medication(s) at V2. Excluded medications require an adequate washout (≥ 5 half-lives) prior to V2. The list of excluded medications is provided separately from the protocol.
11. Evidence of significant active or unstable psychiatric disease by medical history, such as bipolar disorder, schizophrenia, personality disorders or other serious mood or anxiety disorders. Patients with major depressive disorder or generalized anxiety disorder, whose disease state is considered stable and expected to remain stable throughout the course of the study, in the opinion of the investigator, may be considered for inclusion if they are not on excluded medication(s).
12. Are considered by the investigator to be at significant risk for suicide.
13. Women who are pregnant or nursing.
14. Any of the following cardiovascular-related conditions are exclusionary:
 - a. Since enrolling in Study CGAL or Study CGAM or prior to V2 (enrollment), have ECGs showing acute abnormalities of:
 - i. evidence of delayed ventricular repolarization including but not limited to a corrected QT (Fridericia's QT interval [QTcF]) interval >470 msec for women and >450 for men, **and/or**
 - ii. evidence of atrioventricular (AV) depolarization of PR >220 , or conduction delay of QRS >120 , **and/or**

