 - iii. evidence of ischemia or any of the qualitative findings indicative of ST or J-point elevation, excluding those findings consistent with early repolarization (non-ischemic).

NOTE: Patients who meet 1 of the 14(a) ECG criteria during Study CGAL or Study CGAM may enroll in Study CGAR if the study investigator deems the finding not clinically significant.

- b. History of myocardial infarction (MI), unstable angina (UA), percutaneous coronary intervention, coronary artery bypass graft, deep vein thrombosis/pulmonary embolism since enrolling in Study CGAL or Study CGAM and prior to V2 of Study CGAR, or have planned cardiovascular surgery or percutaneous coronary angioplasty or surgery for peripheral arterial disease.
- c. Any lifetime history of vasospastic angina or stroke, or history of emergency room visit for chest pain in which an ischemic or cardiac event was not ruled out since enrolling in Study CGAL or Study CGAM and prior to V2 of Study CGAR.
- d. Clinical evidence of peripheral vascular disease (e.g., Buerger's Disease) or a diagnosis of Raynaud's Disease or Raynaud's Phenomenon.
- e. Have any history of intracranial or carotid aneurysm, intracranial hemorrhage, or stroke.
- f. Have uncontrolled high blood pressure characterized by systolic blood pressure >160 mmHg or diastolic blood pressure >100 mmHg on 2 or more blood pressure assessments prior to V2 of Study CGAR.

NOTE: Patients who meet the 14(f) blood pressure criteria during Study CGAL or Study CGAM may enroll in Study CGAR if the study investigator deems the finding not clinically significant.

15. Any of the following medical conditions are exclusionary:

- a. Have a lifetime history of seizures (except for childhood febrile seizures).
- b. Have a history or presence of any other medical illness including but not limited to any cardiovascular, hepatic, respiratory, hematological, endocrine, psychiatric or neurological disease, or any clinically significant laboratory abnormality, that in the judgment of the investigator indicates a medical problem that would preclude study participation.
- c. Prior to V2, patients who have an elevation of $\geq 2\times$ the upper limit of normal (ULN) for alanine aminotransferase (ALT), or $\geq 1.5\times$ ULN for total bilirubin (TBL) or alkaline phosphatase (ALP) may be retested. The patient's results must be discussed with Lilly Medical and judged not clinically significant prior to enrollment.

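### One tracing with QRS of 120 ms or more removes all of a patient's QT/QTc data, so the QTcF analysis set depends partly on a post-dose outcome

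*SAP*

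**What the plan says.** The rule is in SAP 5.16.7: "For patients with QRS ≥ 120 milliseconds at any time during the study, the QT and QTc interval will be excluded from the analyses". The unit is the patient and the window is the study. It is not limited to the affected tracing, to baseline, or to the analysis period being summarised.

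The same section makes QRS an outcome: "The number and percent of patients meeting criteria for treatment-emergent abnormalities in ECG intervals (PR, QRS, and QTcF) and heart rate will be summarized". QRS High is set at ≥120 ms in Table CGAR.5.2, the same cut-off as the exclusion. The denominators are defined separately. For high values: "For treatment-emergent high analyses: patients with normal or low values at baseline (no high values) will be included". For QTcF increases: "For treatment-emergent increase analyses: patients with a baseline and at least one postbaseline result will be included". ECG baseline is the last non-missing value in the baseline period.

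SAP 5.4 and 5.16 ask for safety analyses over two windows: GMB-treated time, and GMB-treated plus off-treatment time. In the first, only what happens in treated time counts as postbaseline.

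At entry, Protocol 6.2 criterion 14(a)(ii) excludes "or conduction delay of QRS" above 120. A note says that patients with such a finding in a parent study "may enroll in Study CGAR if the study investigator deems the finding not clinically significant".

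Neither document plans a count, a listing or a sensitivity analysis for patients removed by the QRS rule.

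**The concern.** A wide QRS lengthens QT, so QTc from that tracing is hard to interpret. That is a plausible reason to set the tracing aside, although the SAP gives no reason. It does not extend to the patient's other tracings, where QRS is narrow and QTcF is interpretable.

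Because the rule looks at the whole study, who is in the QTcF analysis is decided partly by what happens after dosing. A patient who develops QRS High leaves the numerator and denominator of every QTcF row: low, high, above 500 ms, and the increases above 30, 60 and 75 ms. A QTcF outlier already recorded on a valid tracing disappears from the summary, and the reader is not told how many patients this affects. Safety is the primary objective and ECGs are a listed safety summary, so the analysis set should be one that a reader can reconstruct.

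**Working it through.** **Reading the rule.** Take a patient with narrow QRS up to Month 24, QTcF above 500 ms at Month 12, and QRS ≥120 ms at Month 30.
- QRS High: counted, if QRS was not high at baseline.
- Qualitative shift table ("A shift table summary of qualitative ECGs at any time will be produced", with conduction among its categories): the patient stays in.
- QTcF above 500 ms: not counted, and not in the denominator, although the Month 12 tracing was valid.
- If the Month 30 tracing falls in off-treatment time, the Month 12 value is also lost from the GMB-treated-time table. Under SAP 5.4 the Month 30 tracing would not itself count as postbaseline there.

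**Before or after dosing.** Criterion 14(a)(ii) screens out QRS above 120 before V2, so most triggering tracings should come after dosing. Two pre-dose routes remain. A QRS of exactly 120 ms passes entry but meets the SAP trigger. A waived parent-study finding may also carry over, since the last parent-study ECG can serve as the Visit 1 ECG.

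**Number of ECGs.** Protocol Table 2.1 schedules ECGs at Visit 1, Month 0, Month 6 and every 6 months, and at the first visit after a dose when dosing pauses. They are also required before re-initiation. Visit 1, Month 0 and Months 6 to 36 give 2 + 6 = 8. Continuing to Month 48 gives 2 + 8 = 10.

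**Illustration 1: how many patients could be dropped.** The plan has no figure to reproduce, and the rates here are assumed. If each tracing has probability p of QRS ≥120 ms, independently, a patient with k tracings is dropped with probability 1 − (1 − p)^k.

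| p (assumed) | k = 3 | k = 8 | k = 10 |
|---|---|---|---|
| 0.5% | 1.5% | 3.9% | 4.9% |
| 1% | 3.0% | 7.7% | 9.6% |
| 2% | 5.9% | 14.9% | 18.3% |

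For example, 1 − 0.99^8 = 7.7%. For a given p these are upper bounds, because QRS width is likely to be correlated within a patient. At the other extreme, where all of a patient's tracings are wide or none is, the share is p whatever k is.

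The like-for-like comparison with a tracing-level rule is in tracings. With p = 1% and k = 8 for everyone, the patient-level rule deletes 7.7% of tracings and a tracing-level rule deletes 1.0%. The difference, 7.7 − 1.0 = 6.7% of tracings, is valid narrow-QRS data. Under perfect correlation the difference is zero.

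**Illustration 2: effect on the reported percentage.** Let q be the share of patients dropped, a the QTcF outlier rate in those kept, and b the outlier rate on the dropped patients' narrow-QRS tracings. The SAP rule reports a. With those tracings restored the rate is (1 − q)a + qb. With a = 2%:
- q = 5%, b = 0: 0.95 × 2% = 1.9%
- q = 5%, b = 2%: 2.0%
- q = 5%, b = 25%: 1.9% + 1.25% = 3.15%
- q = 5%, b = 50%: 1.9% + 2.5% = 4.4%
- q = 2%, b = 25%: 1.96% + 0.5% = 2.46%
- q = 2%, b = 50%: 1.96% + 1.0% = 2.96%

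The SAP rule shows 2.0% in every case. The sign of the difference depends on b, and the documents give neither q nor b.

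**The case against.** The strongest case against has five parts.

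- **Nothing is hidden.** QRS High and the conduction shift are reported with the patient included. Protocol 9.4.1 also provides for site reading, central overread and review of alert reports, outside the SAP rule. This stands for the conduction finding. None of it puts a QTcF value back into the QTcF rows.
- **No bias has been shown.** A reader might infer that the rule makes the QTc summary look clean. The documents do not support that. It would require dropped patients to have more QTcF outliers on their narrow-QRS tracings than other patients have, and there are no data on this.
- **The illustrative rates have no source.** This stands. The rates of 0.5% to 2% are assumptions and independence overstates the loss. Counting the pre-dose tracings at the same rate also overstates it, given the entry criterion.
- **The 14(a) note adds little.** A reader might infer that many patients enter with a wide QRS. The waiver needs the investigator's judgement, and a parent-study tracing is not clearly within this study unless it doubles as Visit 1. If the wide QRS persists, a tracing-level rule would drop most of those values as well.
- **Consistency.** The SAP revision history says that the ECG section was added in Version 3 to match the SAPs of the other Phase 3 cluster headache studies, and SAP 5.16 refers to integrated analyses. Those SAPs are not available here. This is a good reason to keep the patient-level summary alongside, but not to make it the only one.

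A looser reading, that patients here means tracings, does not fit the phrase covering the whole study. If tracings were meant, the sentence still needs correcting.

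**Conclusion.** The point holds as a defect in how the QTcF analysis set is defined. The wording is plainly at patient level and covers the whole study, its trigger coincides with a treatment-emergent outcome in the same table, and nothing elsewhere in the documents restores the lost values. The consequence is certain for any patient affected: valid QTcF data leave both numerator and denominator, and an off-treatment tracing can remove treated-time data.

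How many patients are affected, and whether the reported percentages move up, down or not at all, cannot be determined from the documents. The illustrations show only that the loss can grow with follow-up and that the SAP figure would not reveal a difference if there were one. The study is single-arm, and QTc is not among its primary, secondary or tertiary endpoints. This is a correction worth making because it is cheap, not a threat to the main conclusions.

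**What to change.** In SAP 5.16.7, replace the patient-level exclusion with the following:

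1. Exclude QT and QTc only for individual tracings with QRS ≥120 ms, and analyse the patient's remaining tracings.
2. Define baseline QTcF as the last baseline-period tracing with QRS <120 ms. Leave patients with no such tracing out of the QTcF increase analyses. The QTcF high and low rows also depend on baseline status, so say that they use the same baseline.
3. Report the number of patients and tracings excluded, separately before and after baseline.
4. Keep the patient-level exclusion as a secondary summary, for consistency with the parent-study SAPs.

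The cost is one additional table, a few lines of SAP text and a tracing-level filter in the program. It uses data already collected.
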